#### 2.3.1.2 MPI for CC

[name] is Leader of the Clinical Operations Group. Responsibilities include:

1. [name] will interact with the CHILL-pilot study coordinator, [name], to:
  - a. oversee efficient operation of the Participating ICUs, and to
  - b. ensure that all members of the Chill-pilot Clinical Team (e.g. Pulmonary and Critical Care fellows; cross-covering coordinators) are appropriately trained in CHILL-pilot study protocols.
2. Will adjudicate AEs and SAEs with [name] and assist in preparing reports for the DSMB

### 2.3.1.3 MPI for DC

The MPIs for the Data Management and Analysis Core (DC) are [name], CM, MPH and [name]. Responsibilities include:

1. [name] will oversee activities of the DC, including the Biostatistics and Data Management Group
2. [name] will lead the Biostatistics and Data Management Group.
3. [name] will be responsible for designing and executing all statistical analyses.
4. DC offices are collocated in Howard Hall near [name], CHILL-pilot Clinical Research Specialist.
5. Under [name] direction, [name] will produce CHILL-pilot Data and Safety Monitoring reports for [name]
6. DC's physical and administrative separation from the CC is an essential part of the CC/DC "firewall."

### 2.3.2 Coinvestigators

Coinvestigators from within the Division of Pulmonary and Critical Care Medicine (PCCM) and outside the division will have the following responsibilities:

1. Maintaining education and study procedure competency in their respective units
2. Assisting in the screening and enrollment of study participants from the participating units.
3. Assisting in obtaining informed consent.
4. Interpretation of clinical data (medical history, physiologic, laboratory, and radiographic) related to all study procedures (screening, enrollment, data recording, AE/SAE reporting).
5. Order-writing and implementation of study procedures
6. Being available to unit staff for study-related questions
7. Identification of protocol deviations and other reportable events and their correction
8. Identification of AEs/SAEs and assisting in their reporting
9. Assisting in obtaining and handling of biological specimens

### 2.3.3 Coordinators

[name], RRT, MBA is the lead study coordinator and will oversee a coordinator team that includes [name] and a team of pulmonary and critical care fellows.

Responsibilities include:

1. Preparing and maintaining regulatory documents
2. Screening, enrollment, and randomization in all study units
3. Obtaining informed consent from participant or their legally authorized representatives (LAR).
4. Completion of case report forms (CRFs)
5. Identification of protocol deviations and their correction
6. Identification of AEs/SAEs and reporting
7. Obtaining and handling of biological specimens
8. Preparing data summaries for analysis

## 9. Preparing reports for the DC, DSMB, and the IRB

### 2.3.4 Other

## 3/ Participant Recruitment

### 3.1/ Screening

All patients 18-65 years old in one of the study ICUs with a confirmed diagnosis of COVID-19 within the last 3 weeks and on mechanical ventilation less than or equal to 7 days will be screened using the On-line Screening Log, which assigns the 3-digit Study ID and 3-letter patient identifier and stores the patients' demographic information, final status (enrolled or excluded) and, if applicable the reason.

#### Checking/updating patient census:

1. In Epic, under lists, click on a list called "CHILL Screening." You will see all patients in the MICU and CCRU (T6S BCU) with information required for CHILL screening.
2. Go to "Screener Signout sheet" tab.
3. Put in date and time and your name (from pulldown menu).
4. Update census by adding new names and deleting those patients who were discharged/transferred from the unit. Put in patient study status from Pulldown menu. "Never eligible" means that the patient is out of the age inclusion criteria or has been ventilated for > 7 days. "Not eligible" means not currently eligible but could be in future (not yet on mechanical ventilation).
5. Check those patients who were "not eligible" at the previous screen (you can ignore the patients who are "never eligible").

#### Initial Patient Data Entry using on line screening tool:

1. Go to Microsoft 365 and log in using UMB sign on information, then open One Drive. You should see a few Excel programs. There is a COVID\_CHILL\_Assignment tool and a CHILL\_COVID\_Online\_Screening tool as well as Demo versions of each (to practice with).
2. Select "CHILL\_COVID\_Online\_Screening\_Log\_1.0," click on the 3 vertical dots next to the file title, select "Open" and then on "Open in app." If opening on a Mac, you will be given the option to enable macros. On a PC, you will have to manually enable macros once the file is open using the following steps:
  - a. Once the file is open, click on the "File" tab
  - b. Click on the "Enable Content" icon (upper left)
  - c. Click on "Advanced Options"
  - d. Select "Enable Content for this Session."
  - e. The programs should the work.
3. Go to "Sheet1" tab.
4. To enter a new patient and obtain a 3-digit study number and a 3-letter patient identifier, first ensure that the patient has not been previously screened by clicking on Sheet 1 and using the Excel find tool to check for the patient's MRN number.
5. If the patient has not been previously screened, click on "Sheet2" tab.
6. Push the "Push to Start" button. All cells should empty

7. Enter your name from the pulldown menu, the Patients name (Last, first), MRN number, Medical Unit (from the pulldown menu) and room number where they are currently located or are being immediately being transferred to.
8. If you know whether they are enrolled or excluded at this time, you can add this from the pulldown menu. If excluded indicate the reason from the pulldown menu. If multiple reasons, select “multiple exclusions” from the end of the pulldown menu. If you do not know the final status at this time, you can add it later. If you leave a required field empty the program will let you know.
9. Push the “Push button for study number and ID” button. The 3-digit number and 3-letter patient identifier are indicated in cells B14 and B15. Record them on the Screening/Enrollment/Randomization CRF. All data and date/time stamped are recorded on Sheet 1.
10. All data are automatically saved and the sheet locked so you just have to click on the close button.

#### Subsequent Entry of Final Status:

1. If you did not enter the final status when first obtaining patient study ID number and 3-letter identifier, click the “Push to Start” button on Sheet 2.
2. Enter the patient 3-digit study number and 3-letter patient identifier in cells B21 and C21. Make sure the 3-letter identifier is in ALL CAPS. If you don’t have immediate access to the number/letter ID, you can find them on Sheet 1.
3. Enter the Final Status and Reason for Exclusion if applicable from the pulldown menus. If multiple exclusions, select “multiple exclusions” from the end of the pulldown menu.
4. Push the “Push button to enter final status” button.
5. If the number and 3-letter ID match, you will get a message that the information has been added; otherwise you will get a message that there is a mismatch. In this case, check the number and letters and make sure letters are in ALL CAPS and push the button again.
6. All data are automatically saved and the sheet locked so you just have to click on the close button.

If you make a mistake with data entry on sheet 1, make sure you use the correct patient number/3-letter code in the sequence and let me know so I can fix any errors (e.g double entry).

## 3.2/ Enrollment

### 3.2.1 Inclusion Criteria

1. COVID-19 diagnosed by PCR within 3 weeks
2. men and women
3. any race/ethnicity
4. 18-65 years of age
5. endotracheal tube or tracheostomy in place and mechanically ventilated for < 7 days;

6. radiologic evidence of bilateral pulmonary infiltrates not fully explained by hydrostatic pulmonary edema
7. access to an LAR to provide consent (remote consent is permissible).

### 3.2.2 Exclusion Criteria

1. Missed ARDS window (>48hrs)
2. Missed mechanical ventilation window (>7 days)
3. Refractory hypotension (> 0.2 mcg/kg/min of norepinephrine or equivalent dose for minimum of 6 h)
4. Core temperature <35.5°C while not receiving CRRT
5. Patient is unable to give consent and no legally authorized representative is available;
6. Significant, active bleeding (>3u blood products and/or surgical/IR intervention)
7. Platelets <10K/mm^3 (uncorrected)
8. Active hematologic malignancy
9. Skin process precludes cooling device
10. Moribund, not likely to survive 72h
11. Pre-morbid condition makes it unlikely that patient will survive 28 days
12. Do Not Resuscitate status
13. Not likely to remain intubated for ≥48h
14. Physician unwilling to participate
15. Severe underlying lung disease
  - a. On home O2
  - b. On BIPAP (except for OSA)
  - c. Prior lung transplantation
16. BMI >45 kg/m^2
17. Known NYHA class IV heart disease
18. Acute Coronary Syndrome past 30 days (MI, unstable angina)
19. Cardiac arrest within 30 days of enrollment
20. burns over >20% of the body surface
21. severe chronic liver disease (Child-Pugh of 12-15)
22. Previously randomized in CHILL study

### 3.3/ Randomization

Subjects will be stratified by proning status at enrollment and randomized within each stratum to receive TH or usual temperature management using a 1:1 assignment ratio. Treatment group assignment will be made using an Excel-based assignment tool stored on the UMB Microsoft OneDrive, which records date, time, and investigator who makes the treatment assignment. Baseline APACHE II, Sequential Organ Failure (SOFA) score 3, driving pressure, P/F ratio, and oxygen saturation index will be documented at time of randomization to assess comparability of disease acuity between groups.

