
We have been approved for funding by Department of Defense (DoD) to support for a 4-year multicenter RCT of TH+NMB for 48h vs. standard of care with contract to be completed June 1, 2020 and with enrollment to begin in Fall of 2020. This study was designed prior to the onset of COVID-19, which is now the most common cause of ARDS and will likely continue to be in the Fall, 2020 and perhaps beyond. Therefore, it is important to decide whether patients with COVID-19 ARDS should be enrolled in our CHILL trial. Therefore, we will conduct a 20-patient pilot safety and feasibility trial of our CHILL TH+NMB treatment vs. control in COVID-19 patients with ARDS who meet the inclusion/exclusion criteria of our DoD-funded trial. The major objective of the proposed pilot trial is to determine whether it is safe and feasible to include patients with COVID-19 ARDS in our Phase IIb CHILL RCT of TH+NMB vs. control in patients with moderate to severe ARDS.

The pilot will be conducted at the University of Maryland Medical Center. To facilitate randomization within the inclusion window, we will consent and enroll based on partial fulfillment of randomization criteria and randomize once all criteria are met. Patients will be

eligible for enrollment when they have been diagnosed with COVID-19 by PCR, and have met all Berlin criteria for moderate to severe ARDS within the 48h inclusion window except the P/F ratio  $\leq 200$  but will not be randomized until P/F ratio (measured or imputed based on SpO2) is  $\leq 200$  (while on  $\geq 8$  cm H2O PEEP and  $\geq 0.6$  FiO2). We plan to randomize a total 20 patients over 4 months to hypothermia (core temperature 34°-35°C for 48h) plus NMB or usual temperature management. The primary outcome measures will be effectiveness of cooling in achieving and maintaining the target temperature and safety measures. Secondary outcomes will include 28-day ventilator-free days (VFDs), 28-day ICU-free days, oxygen saturation index (OSI), driving pressure, Sequential Organ Failure Assessment (SOFA) score, 60-day and 90-day survival, 90-day functional assessment, cognitive assessment at ICU and hospital discharge, and biomarkers of inflammation and lung injury. Since the nature of the intervention precludes blinding, all treatment and clinical decision making related to study outcomes will be protocolized and compliance with study protocols will be monitored.

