3.3.2 Randomization Procedures

Randomization will be performed by a macro-driven Excel spreadsheet (CHILL\_COVID\_Assignment\_Tool 1.0) stored on the UMB Microsoft OneDrive:

1. Select “CHILL\_COVID\_Assignment\_Tool 1.0,” click on the 3 vertical dots next to the file title, select “Open” and then on “Open in app.” If opening on a Mac, you will be given the option to enable macros. On a PC, you will have to manually enable macros once the file is open using the following steps:
  - a. Once the file is open, click on the “File” tab
  - b. Click on the “Enable Content” icon (upper left)
  - c. Click on “Advanced Options”
  - d. Select “Enable Content for this Session.”
  - e. The programs should the work.
2. On Sheet 1, Push “Push to Start” button
3. Enter your name from pulldown menu and push “Push to Start” button

4. Enter 3-digit study ID number from pulldown menu and push “Push to Start” button.
5. Re-enter 3-digit study ID number from pulldown menu and push “Push to Start” button.
6. If numbers do not match you will get an error message.
7. Otherwise enter 3-letter identifier and push “Push to Start” button.
8. Enter proning status from pulldown menu and push the “Confirm proning status, then push this button to get assignment” button.
9. The treatment assignment will be displayed in cell B12, all information will be entered along with date/time stamp on Sheet 2.
10. All data are automatically saved and the sheet locked so you just have to click on the close button.

If you make a mistake, make sure you the correct treatment assignment right away and let me know about the entry error so I can fix it. If you put in the wrong proning status, repeat with correct status and let me know so I can fix the error. If you entered wrong patient number or 3-letter code, use the treatment assignment provided and let me know so I can fix the error.

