### 5/ Subject Enrollment and Randomization Procedures

If the patient meets the P/F ratio criterion for randomization (from ABG or imputed from SpO2), they will be randomized simultaneously with enrollment. Otherwise their P/F ratio will be followed until it is <200 or they exit the 48h ARDS window. If the patient meets the P/F ratio criterion within the ARDS window, mark the “Yes” box about randomization on line 12, otherwise check the “No” box. If the patient is randomized, collect the baseline blood sample, obtain the treatment assignment using the on-line assignment tool, enter the randomization date and time on line 14 and the treatment assignment on line 15. Once Randomized, baseline information will be recorded on the Baseline Data CRF and, if assigned to the Therapeutic Hypothermia arm, sedation, NMB, and cooling will begin as soon as possible.

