- Monitor for qualifying P/F ratio using the P/F ratio table. For each ventilator day, check the appropriate “Yes/No” box for PEEP $\geq$ 8 cm H2O, whether P/F $<$ 200, whether the value was calculated from the measured PaO2 (“M”) or imputed (“I”) from the SpO2. Record the value for the P/F ratio and the date and time it was measured. If patient meets all Berlin criteria, including P/F ratio  $<$  200 within 7 days of onset of intubation/mechanical ventilation, check the “Yes” box on line 14, collect the baseline blood sample, and proceed with randomization; otherwise, check the “No” box and STOP.
- If randomizing, record whether the patient is receiving intermittent prone positioning at the time of randomization on line 15.
- Obtain the treatment assignment using the on-line assignment tool, record the randomization date and time on line 16 and record the treatment assignment on line 17.
- For patients randomized to the cooling arm, initiate sedation, NMB, and cooling.

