**eTable 2: Imputed PF ratio (cells) for combinations of SpO2 (rows) and FiO2 (columns)**

	0.30	0.35	0.40	0.45	0.50	0.55	0.60	0.65	0.70	0.75	0.80	0.85	0.90	0.95	1.00
80%	148	127	111	98	89	81	74	68	63	59	55	52	49	47	44
81%	151	129	113	101	91	82	76	70	65	60	57	53	50	48	45
82%	155	132	116	103	93	84	77	71	66	62	58	55	52	49	46
83%	158	136	119	106	95	86	79	73	68	63	59	56	53	50	47
84%	162	139	122	108	97	89	81	75	70	65	61	57	54	51	49
85%	167	143	125	111	100	91	83	77	71	67	63	59	56	53	50
86%	171	147	129	114	103	94	86	79	73	69	64	61	57	54	51
87%	177	151	132	118	106	96	88	81	76	71	66	62	59	56	53
88%	182	156	137	121	109	99	91	84	78	73	68	64	61	58	55
89%	189	162	141	126	113	103	94	87	81	75	71	67	63	60	57
90%	196	168	147	130	117	107	98	90	84	78	73	69	65	62	59
91%	203	174	153	136	122	111	102	94	87	81	76	72	68	64	61
92%	213	182	159	142	128	116	106	98	91	85	80	75	71	67	64
93%	223	191	168	149	134	122	112	103	96	89	84	79	74	71	67
94%	236	202	177	157	142	129	118	109	101	94	89	83	79	75	71
95%	252	216	189	168	151	138	126	116	108	101	95	89	84	80	76
96%	273	234	205	182	164	149	136	126	117	109	102	96	91	86	82

Conditions required to use inferred P/F ratio include: (a) SpO2 values 80-96%, (b) SpO2 measured ≥10 min after FiO2 change, (c) PEEP ≥ 8 cm H2O, (d) adequate pulse oximeter wave form, and (e) qualifying inferred P/F ratio is confirmed 1-6 hrs after the initial determination.

P/F ratio criterion met within 7 ventilator days

- Yes Collect **baseline blood sample**, randomize and record randomization time and treatment assignment below
- No STOP

Is this patient currently receiving prone positioning alternating with supine positioning?

- Yes
- No

Randomization date/time:    /   /          
MONTH D D Y Y Y Y TIME (0-2400)

Treatment assignment (check one)

- Therapeutic Hypothermia
- Usual Treatment

Initiate sedation, NMB, and cooling protocol for subjects randomized to Therapeutic Hypothermia

Complete Baseline information CRF.

See schedule for first week blood and data collection below.

--	--

[figure not shown]
SITE ID

--	--	--	--

PATIENT ID

--	--	--

LETTER CODE

- Collect baseline blood and complete Baseline CRF based on 24h preceding randomization
- Collect day 1 blood and complete Day 1 CRF at 0800 on randomization day + 1; (the duration of day 1 may be 8h 1 min to 31h 59 min as indicated by the examples a - c)

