Unassisted breathing for  $\geq 48$  hours by day 28?  Yes  No

If Yes, enter first date UAB began: 

MONTH			D	D	Y	Y	Y	Y

Was patient extubated by day 28?  Yes  No

If Yes, enter date of extubation: 

MONTH			D	D	Y	Y	Y	Y

Did the subject undergo tracheostomy by day 28?  Yes  No

If Yes, enter date of tracheostomy: 

MONTH			D	D	Y	Y	Y	Y

Was the patient discharged/transferred to a non-ICU setting by day 28?  Yes  No

If Yes, enter date of discharge/transfer: 

MONTH			D	D	Y	Y	Y	Y

Was the patient receiving prone positioning at randomization?  Yes  No

If Yes, Study day when patient received final prone positioning: 

--	--

If No, did patient receive proning during the first 28 study days:  Yes  No

If Yes, study day proning started 

--	--

 and ended 

--	--

SITE ID		PATIENT ID				LETTER CODE			

**Ventilator days until UAB at home, death or day 90 is any day patient received assisted breathing except for <24hr related to procedure/surgery**

Patient achieved UAB?  No  Yes Date of 1st UAB: 

MONTH			D	D	Y Y Y Y				

Patient returned to assisted breathing  No  Yes Date of return to AB: 

MONTH			D	D	Y Y Y Y				

Patient achieved UAB again?  No  Yes Date of 2nd UAB: 

MONTH			D	D	Y Y Y Y				

Patient returned to assisted breathing again  No  Yes Date of return to AB: 

MONTH			D	D	Y Y Y Y				

Patient achieved UAB again?  No  Yes Date of 3rd UAB: 

MONTH			D	D	Y Y Y Y				

Patient returned to assisted breathing again  No  Yes Date of return to AB: 

MONTH			D	D	Y Y Y Y				

Patient achieved UAB again?  No  Yes Date of 4th UAB 

MONTH			D	D	Y Y Y Y				

- End of life decision making (for all pts alive and dead)
- No DNR decision made
  - DNR decision made-withhold only CPR (CR or PR)
  - DNR decision made-withhold life support and CPR
  - DNR decision made-withdraw life support
  - Diagnosis of brain death
  - Unknown/can't tell

- Was written consent obtained from the subject during hospitalization?  Yes  No, reason
- patient died
  - Patient never regained decision-making capacity
  - Patient declined further participation in study
  - Other

Did patient require dialysis during Study hospitalization?  Yes If yes, enter dates of first and last dialysis: Date of first dialysis: \_\_\_\_\_ Date of last dialysis: \_\_\_\_\_  No

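### The stratification factor is proning status at enrolment in Section 3.3 but at randomisation on the forms; fix it at one time point

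*Protocol*

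**What the plan says.** Protocol Section 3.3 defines the factor by status at enrolment: "Subjects will be stratified by proning status at enrollment and randomized within each stratum", with 1:1 assignment within stratum.

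Three other places use randomisation. The instructions in Section 10.1 tell staff to "record whether the patient is receiving intermittent prone positioning at the time of randomization on line 15". Line 15 of the Screening/Enrollment/Randomization form asks "Is this patient currently receiving prone positioning alternating with supine positioning", and sits between the line confirming the P/F criterion and the line for the randomisation time. Line 14 of the Summary of Patient Outcomes asks "Was the patient receiving prone positioning at randomization".

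The stratum is actually set in Section 3.3.2, step 8, which says "Enter proning status from pulldown menu and push the" confirmation button. No time point is given.

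The two events are distinct by design. Section 1.1 says "we will consent and enroll based on partial fulfillment of randomization criteria and randomize once all criteria are met". Under Section 5, patients whose P/F already qualifies are treated without a gap: "they will be randomized simultaneously with enrollment". For the rest: "Otherwise their P/F ratio will be followed until it is <200 or they exit the 48h ARDS window".

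**The concern.** If enrolment and randomisation were the same moment, the difference in wording would be harmless. They are not, so one factor has two definitions, and a patient whose proning status changes between them belongs to a different stratum under each. The stratum decides which assignment list is used.

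Three things are at stake. Section 1.1 names prone positioning among the measures that limit injurious ventilation, so it is a relevant co-treatment for ventilator-free days, oxygen saturation index and driving pressure. Stratifying on an earlier status forces balance on that earlier status rather than on status at treatment start. Second, Section 2.2.1.2.1 has the stratum and assignment list checked monthly against the randomisation schedules and used to confirm agreement with site documents; a stratum based on enrolment can disagree with line 15. Third, the closing paragraph of Section 3.3.2 tells a user who entered the wrong proning status to repeat the procedure with the right one. That is a second draw after the first assignment has been displayed, in a trial that Section 1.1 says cannot be blinded. Without a time point, whether an entry was wrong is open to argument.

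**Working it through.** The plan states no figure on this point, so there is nothing to reproduce. The check sets the passages side by side.

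**1. Time point of the factor**

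| Place (Protocol) | Proning status taken at |
|---|---|
| Section 3.3 | enrolment |
| Section 3.3.2, step 8 (sets the stratum) | not stated |
| Section 10.1, instruction for line 15 | randomisation |
| Randomisation form, line 15 | now, just before assignment |
| Summary of Patient Outcomes, line 14 | randomisation |

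Section 3.3 is unlikely to be using the two words interchangeably. Two sentences later it places the baseline severity measures at randomisation.

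**2. Length of the gap**

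- 0 h if P/F already qualifies (Section 5).
- Up to 48 h by Section 5; the schedule in Section 6 agrees, with enrolment under day -2 and randomisation under day 0.
- Possibly longer. Section 10.1 and form line 14 let P/F qualify at any time within 7 ventilator days. The form's exclusion list defines its 48 h limit by ARDS with P/F already below 200, so that limit does not bound a wait for P/F to fall.

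**3. Who is classified differently**

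| | Status unchanged | Status changed |
|---|---|---|
| Randomised at enrolment | same stratum | no interval in which to change |
| Randomised later | same stratum | **different stratum** |

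Only one cell is affected.

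**4. Scale, by assumption only**

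Let p be the share of randomised patients in that cell. The documents do not give p. With N = 20 (Section 1.1) and independent patients, the expected number is 20p and the chance of at least one is 1 - (1 - p)^20.

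| Assumed p | Expected number | Chance of at least one |
|---|---|---|
| 1% (10% wait x 10% change) | 0.2 | 1 - 0.99^20 = 18% |
| 2% | 0.4 | 1 - 0.98^20 = 33% |
| 5% | 1.0 | 1 - 0.95^20 = 64% |
| 10% | 2.0 | 1 - 0.90^20 = 88% |
| 20% | 4.0 | 1 - 0.80^20 = 99% |

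The range runs from probably nobody to several patients. It shows only that a discordance of a few per cent is enough to make the question arise in practice.

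**5. Can the Section 3.3 stratum be checked afterwards?**

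Only in part. The randomisation form has no enrolment date or time and no proning status at enrolment. Baseline Data line 32 records when a proning protocol began, and consent signatures are dated (Section 3.4).

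**The case against.** The strongest reply is that the procedures already settle the matter. The stratum is set only when the assignment is drawn. The button in step 8 asks the user to confirm proning status first. Line 15, answered just before, asks about the patient's current status, and no form asks for a yes/no status at enrolment. Someone following the forms would naturally enter the line 15 answer. This carries weight: users may never split between the two readings. But step 8 does not say so, and the section that defines the randomisation says something else.

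The reply is also right about the size of the harm. Both time points precede assignment, so either gives a valid 1:1 randomisation within stratum. The SAP names no stratum term: the primary outcome is descriptive, serious adverse events are compared by chi-square, and ventilator-free days by a permutation test on the difference in means.

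Some stronger readings are tempting but unsupported:

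- A reader might infer that every patient who waits is misclassified. Only those who wait and also change status are.
- A reader might infer that proning is likely to start in this gap because P/F is falling. The documents state no criterion for starting proning and no P/F trigger for it. Line 15 also asks about alternating positioning, so a patient who is supine at that moment can still be a yes.
- A reader might infer that the arms will be unbalanced on proning. Balance at treatment start is less tightly forced, but still expected on average.

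**Conclusion.** The inconsistency is real and sits in current text: one stratification factor has two time points, and the step that applies it names neither. The consequence is modest. It is limited to patients who wait and change proning status, and the documents give no basis for counting them. The mismatch in wording does not by itself bias the comparison, and no analysis in the SAP uses the stratum.

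The main reason to correct it is operational. With no defined time point, a patient whose status changed could be entered either way, and either entry could later be called wrong. Under Section 3.3.2 that leads to a second draw with the first assignment already known. Looser balance and disagreement between the tool and line 15 come second. The documents do not show that any of this would happen; they leave it possible.

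Nor should 48 h be read as a firm maximum for the gap, since the 7-ventilator-day wording allows more. Those limits need to be reconciled in their own right, but the conclusion here holds under either.

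**What to change.** Two wording changes:

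1. In Section 3.3, define the factor as proning status at randomisation (form line 15).
2. In Section 3.3.2, step 8, state that the value entered in the tool is the line 15 answer.

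Name the item as well as the line number, because Section 5 numbers the same form differently and gives line 15 as the treatment assignment.

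A useful addition, in the closing paragraph of Section 3.3.2: if the stratum was mis-entered, keep the first assignment and record the error. That paragraph already keeps the assignment given when a patient number or letter code was entered wrongly, so this would make the two cases consistent.

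The cost is a few sentences. Line 15 is already answered just before assignment, so no new data or form is needed. The change concerns only when a stratification variable is read; it does not affect who is proned or when.
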